16.2.2.3. Vital Signs

The analysis of vital signs will focus on clinically relevant abnormalities. The number and percentage of subjects with clinically relevant postbaseline abnormalities will be presented. Summary statistics for actual values and change from Baseline will also be presented.

16.2.2.4. ECGs

ECG results will be presented by subject, and as appropriate, results will be summarized descriptively for each treatment group. The number and percentage of subjects with shifts from baseline normal to each of the categorical values denoting normal, abnormal clinically significant, and abnormal (not clinically significant) will be summarized.

16.2.2.5. Clinical Laboratory Results

Clinical laboratory evaluations, including hematology, blood chemistry, urinalysis, and urine total protein, will be summarized using study visit for each treatment group. These safety variables will also be presented over time after study treatment administration, as appropriate. Laboratory parameters will also be summarized using shift tables, as appropriate.

For urinary protein concentration >0.2 g/L, consider repeat testing and further evaluation.

16.2.2.6. Coagulation Parameters

Coagulation parameters (aPTT, PTT, and INR) will be collected. The coagulation testing must be performed and reviewed prior to dosing.

CONFIDENTIAL

The information contained herein may not be used, disclosed, or published without the written consent of Biogen MA Inc.

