- ⁹ At the evaluations scheduled for injection of study treatment or sham procedure, subjects will be assessed for the following growth parameters: body length, head circumference, chest circumference, and arm circumference.
- ¹⁰ Neurological examinations include assessment of mental status, level of consciousness, sensory function, motor function, cranial nerve function, and reflexes.
- ¹¹ Neurological examinations will occur between 4 to 6 hours after the injection of study treatment or sham procedure.
- ¹² Blood chemistry, hematology, and urinalysis panels.
- ¹³ Samples for safety laboratory tests will be collected before the injection of study treatment or sham procedure on Days 64 and 183 only.
- ¹⁴ End of Part 1 safety laboratory tests may be performed locally in addition to centrally to accommodate the Part 2 Day 1 dosing.
- ¹⁵ Refer to [Table 5](#) for CSF PK sample schedule. The CSF samples will be analyzed for Nusinersen concentrations. The remaining CSF sample will be stored for optional future biomarker analyses.
- ¹⁶ Blood samples for PK assessment will be collected 4 hours (± 1 hour) after the injection of study treatment or sham procedure only on Day 1. Refer to [Table 5](#) for the plasma PK sample schedule.
- ¹⁷ Blood samples for PK assessment will be collected before the injection of study treatment or sham procedure on Days 64 and 183 only. Refer to [Table 5](#) for the plasma PK sample schedule.
- ¹⁸ Overnight stay (at least 24 hours) is required after the first injection of study treatment or sham procedure. Following all subsequent injections or sham procedures, a stay of at least 6 hours at the study site is required; overnight stays are optional on these days.
- ¹⁹ In addition to concomitant medications, ancillary procedures will be recorded.
- ²⁰ AEs and SAEs will be collected in the case report form from the time of signing of the informed consent form as described in [Section 15.3.1](#) and [Section 15.3.2](#).

CONFIDENTIAL

The information contained herein may not be used, disclosed, or published without the written consent of Biogen MA Inc.

4.2.2. Schedule of Events: Part 2

Table 3: Part 2 Schedule of Activities for Subjects Randomized to Receive Nusinersen in Part 1

Study Period	Part 2 Treatment/Follow-Up									
	Study Day	Day 1			Day 2 ¹	Days 120, 239, 358, 477, 596, 715 (± 7 days) ²			Days 121, 240, 359, 478, 597, 716 ¹	Part 2 Final Follow-Up (Day 835 [± 7 days]) ³ or Part 2 Early Termination ⁴

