³ The Part 2 Final Follow-up Evaluation will occur 4 months after the last injection of study treatment, which will either be on Day 716 or later, if Part 2 of the study continues beyond Year 2.

⁴ Subjects who terminate early will be encouraged to complete the safety evaluations scheduled for the Part 2 Early Termination Evaluation.

⁵ Inclusion/Exclusion Criteria, Informed Consent, and CSF PK must be performed on Part 2 Day 1.

⁶ Vital signs include resting systolic and diastolic blood pressure, pulse rate, respiratory rate, temperature, pulse oximetry, and transcutaneous carbon dioxide. Pulse oximetry and transcutaneous carbon dioxide will be measured predose at each evaluation.

⁷ If Part 2 Day 1 study treatment injection is delayed more than 24 hours after the End of Part 1 visit, the following procedures must be done on Part 2 Day 1 predose: vital signs, weight, growth parameters, physical examination, ventilator use, neurological examination, and CSF PK. If Part 2 Day 1 study treatment injection is delayed more than 24 hours after End of Part 1 due to an AE, SAE, or other safety concern, or if Part 2 Day 1 study treatment injection is delayed more than 30 days after End of Part 1 for any reason, the following procedures must be done on Part 2 Day 1 predose: vital signs, weight, growth parameters, physical examination, ventilator use, neurological examination, ECG, CSF PK, and safety laboratory tests. Immunogenicity testing must also be repeated predose if Part 2 Day 1 study treatment injection is delayed more than 30 days after End of Part 1 for any reason.

⁸ Vital signs (resting systolic and diastolic blood pressure, pulse rate, respiratory rate, temperature, and pulse oximetry) will be collected 1 hour (± 15 minutes) after the injection of study treatment.

⁹ At the evaluations scheduled for injection of study treatment, subjects will be assessed for the following growth parameters: body length, head circumference, chest circumference, and arm circumference. Growth parameters and weight are to be collected at the same time.

¹⁰ Neurological examinations include assessment of mental status, level of consciousness, sensory function, motor function, cranial nerve function, and reflexes. If sedation was used, please allow sufficient recovery time for the subject to be fully engaged in the examination because it is important that the data collected truly reflect the subject’s neurological performance.

CONFIDENTIAL

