The information contained herein may not be used, disclosed, or published without the written consent of Biogen MA Inc.

- ¹¹ Predose and postdose.
- ¹² ECG will be performed on Days 239, 477, and 715, and at the Part 2 Final Follow-up Evaluation. ECG must be performed before obtaining blood samples for safety laboratory tests.
- ¹³ Blood chemistry, hematology, urinalysis, urine total protein panels, and coagulation parameters. Urine total protein and coagulation parameters will be assessed by local laboratories.
- ¹⁴ Samples for safety laboratory tests will be collected before the injection of study treatment at each dosing visit.
- ¹⁵ Blood samples for immunogenicity testing will be collected before the injection of study treatment on Days 239, 477, and 715.
- ¹⁶ Refer to [Table 6](#) for CSF PK sample schedule. The CSF samples will be analyzed for Nusinersen concentrations. The remaining CSF sample will be stored for optional future biomarker analyses.
- ¹⁷ Blood samples for PK assessment will be collected 4 hours (± 1 hour) after the injection of study treatment only on Day 1. Refer to [Table 6](#) for the plasma PK sample schedule. Plasma PK samples will be collected predose on Days 239, 477, and 715.
- ¹⁸ The optional assessment of sibling SMA data collection will be performed only after obtaining consent.
- ¹⁹ In addition to concomitant medications, ancillary procedures will be recorded.
- ²⁰ AEs and SAEs will be collected in the case report form from the time of signing of the informed consent form as described in [Section 15.3.1](#) and [Section 15.3.2](#).

CONFIDENTIAL

The information contained herein may not be used, disclosed, or published without the written consent of Biogen MA Inc.

Table 4: Part 2 Schedule of Activities for Subjects Randomized to Receive Sham Procedure in Part 1

Study Period	Part 2 Treatment/Follow-Up															
	Day 1			Day 2 ¹	Day 15 (±1 day)			Day 16 ¹	Day 29 (±1 day)			Day 30 ¹	Days 64, 183, 302, 421, 540, 659, 778 (±7 days) ²			Days 65, 184, 303, 422, 541, 660, 779 ¹
Study Day	Predose ⁵	LP	Postdose		Predose	LP	Postdose		Predose	LP	Postdose		Predose	LP	Postdose	
Informed Consent	X ⁵															
Inclusion/Exclusion Criteria	X ⁵															
Vital Signs ⁶	X ⁷		X ⁸	X ⁹	X		X ⁸		X		X ⁸		X		X ⁸	X
Weight	X ⁷			X	X				X				X			X
Growth Parameters ¹⁰	X ⁷				X				X				X			X
Physical Examination	X ⁷				X				X				X			X
Ventilator Use	X ⁷			X	X			X	X			X	X			X

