² If the study continues beyond Year 2 (i.e., beyond Day 778), then from Day 897 onwards, subjects will maintain evaluations for study treatment injection every 4 months with the schedule of events for those additional timepoints to alternate between the assessments done on Day 183 and those done on Day 302. Day 302 assessments would be performed at Day 897 and Day 183 assessments would be performed at Day 1016. That pattern would continue until the end of the study. Part 2 Final Follow-up Evaluation would then occur approximately 4 months after the last injection of study treatment.

³ The Part 2 Final Follow-up Evaluation will occur 4 months after the last injection of study treatment, which will either be on Day 778 or later, if Part 2 of the study continues beyond Year 2.

⁴ Subjects who terminate early will be encouraged to complete the safety evaluations scheduled for the Part 2 Early Termination Evaluation.

⁵ Inclusion/Exclusion Criteria, Informed Consent, and CSF PK must be performed on Part 2 Day 1 predose.

⁶ Vital signs include resting systolic and diastolic blood pressure, pulse rate, respiratory rate, temperature, pulse oximetry, and transcutaneous carbon dioxide. Pulse oximetry and transcutaneous carbon dioxide will be measured predose at each evaluation.

CONFIDENTIAL

The information contained herein may not be used, disclosed, or published without the written consent of Biogen MA Inc.

- ⁷ If Part 2 Day 1 study treatment injection is delayed more than 24 hours after the End of Part 1 visit, the following procedures must be done on Part 2 Day 1 predose: vital signs, weight, growth parameters, physical examination, ventilator use, neurological examination, and CSF PK. If Part 2 Day 1 study treatment injection is delayed more than 24 hours after End of Part 1 due to an AE, SAE, or other safety concern, or if Part 2 Day 1 study treatment injection is delayed more than 30 days after End of Part 1 for any reason, the following procedures must be done on Part 2 Day 1 predose: vital signs, weight, growth parameters, physical examination, ventilator use, neurological examination, ECG, CSF PK, and safety laboratory tests. Immunogenicity testing must also be repeated if Part 2 Day 1 study treatment injection is delayed more than 30 days after End of Part 1 for any reason.

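### Protocol version 4 wants coagulation tested and reviewed before dosing, but its Part 2 Day 1 schedule lets a site dose without the test

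*Protocol*

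**What the plan says.** All of the following is current Protocol version 4 text. SAP Section 1.4 repeats the same schedule and footnotes.

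- **The rule.** Section 16.2.2.6: "The coagulation testing must be performed and reviewed prior to dosing". No visit is exempted.
- **Where the test sits in Part 2.** There is no separate coagulation row. Safety Laboratory Tests are defined (Table 3 footnote 13, Table 4 footnote 14) as "Blood chemistry, hematology, urinalysis, urine total protein panels, and coagulation parameters".
- **When that row applies on Part 2 Day 1.** In both tables the Day 1 predose cell carries footnote 7, which has two triggers for safety laboratory tests. The first is a safety-related hold, where dosing is "delayed more than 24 hours after End of Part 1 due to an AE, SAE, or other safety concern". The second looks only at the length of the wait, whatever its cause, and applies "if Part 2 Day 1 study treatment injection is delayed more than 30 days after End of Part 1 for any reason".
- **What is unconditional on Day 1.** Footnote 5 of Table 3: "Inclusion/Exclusion Criteria, Informed Consent, and CSF PK must be performed on Part 2 Day 1". Footnote 5 of Table 4: "Inclusion/Exclusion Criteria, Informed Consent, and CSF PK must be performed on Part 2 Day 1 predose".
- **What Part 1 supplies.** Table 2 marks coagulation at Screening only. The Part 1 safety panel, including the End of Part 1 draw, is "Blood chemistry, hematology, and urinalysis panels" (footnote 12).
- **Later Part 2 visits.** Table 3 footnote 14 and Table 4 footnote 15: "Samples for safety laboratory tests will be collected before the injection of study treatment at each dosing visit". These markers are on the later dosing-visit cells, not on Day 1.

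**The concern.** The rule is in the statistical methods chapter, while sites work from the schedule tables. Section 11.3, where a site might look for a pre-injection check, says that the protocol requires no treatment precautions. So the tables have to carry the rule, and on Part 2 Day 1 they do not clearly do so.

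Conditional testing on Day 1 makes sense for chemistry, hematology and urinalysis, because fresh End of Part 1 results can stand in for them. For coagulation no End of Part 1 result is scheduled.

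Day 1 is also where the check matters most for former sham children. Under Section 11.1.2 the sham was a skin prick without needle insertion, so Part 2 Day 1 is their first lumbar puncture in the study.

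**Working it through.** The plan gives no figure to reproduce. The check compares the rule with the schedule, and then works out how old the last scheduled result would be.

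**Step 1. Cases for the Part 2 Day 1 injection, both groups (footnotes 5 and 7).**

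| Timing after End of Part 1 | Predose procedures triggered by footnote 7 | Coagulation required by the schedule? |
|---|---|---|
| Within 24 hours | None | No |
| More than 24 hours and up to 30 days, not for safety | Vital signs, weight, growth, physical examination, ventilator use, neurological examination, CSF PK | No |
| More than 24 hours, for an adverse event or other safety concern | The above plus ECG and safety laboratory tests | Yes |
| More than 30 days, any reason | The above plus ECG, safety laboratory tests and immunogenicity | Yes |

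The first case is a planned route: Section 7.2.2 lets a subject move to Part 2 as soon as the End of Part 1 assessments are done.

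**Step 2. Does the later-visit footnote reach Day 1?** If the sentence in Table 3 footnote 14 and Table 4 footnote 15 governed Day 1, safety laboratory tests would always be due there, and the laboratory triggers in footnote 7 would do nothing. Placement and sense both tie it to the later cells.

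**Step 3. Age of the last scheduled result in the two uncovered cases.** Inputs: Screening from Day -28 to Day -1 (Table 2), no Day 0, End of Part 1 at Day 422 on the full schedule (Table 2 footnote 3). Assume rollover on the same day, Part 1 Day D, and ignore visit windows.

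- Screening on Day -1: age = 1 + (D - 1) = D days.
- Screening on Day -28: age = 28 + (D - 1) = D + 27 days.

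| Rollover day D | Age in days |
|---|---|
| 64 | 64 to 91 |
| 183 | 183 to 210 |
| 422 | 422 to 449 |

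The values of D are illustrations, because actual rollover days are not reported. Day 422 is a ceiling: SAP Section 2 says that Part 1 ended early and that sham subjects left first. In the second case of Step 1, the length of the delay is added to the age.

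**Step 4. How many children.** The planned numbers are 7 sham and 14 nusinersen. The number of Part 2 Day 1 visits held under version 4 is not given, so the range is 0 to 7 former sham children and 0 to 14 former nusinersen children.

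**The case against.** The strongest defence is that the provisions can be read together. Section 16.2.2.6 binds every site, and footnote 7 sets minimum repeats after a delay without waiving anything. On this view a fully compliant site leaves no child untested. That is fair, but it means that the schedule alone does not deliver the check and that the site must notice a sentence in the statistics chapter.

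A second defence is that the rule has no validity window and does not say that a new test is needed for each dose, so a Screening result satisfies it literally. Part 1 itself schedules coagulation at Screening only and then up to six doses. This stands as a limit. A reader might infer that a fresh test is owed before every injection, or that the 30 days in footnote 7 are a shelf life for a coagulation result. Neither is supported: those 30 days run from End of Part 1 to injection.

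Third, other safeguards exist. The Part 2 exclusion criterion asks the Investigator to reassess fitness, including laboratory tests. The Directions for Handling and Administration override the protocol on handling and administration (Section 12) and are not available here, so a pre-puncture check may be written there. This lowers confidence in the practical consequence, though not in the mismatch.

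Fourth, exposure may be nil. Version 4 already reports US and European approval of nusinersen (Section 5.2). SAP Sections 4.5.2 and 4.7 say that WHO milestones and ACEND were collected only after version 4. This suggests, without proving, that version 4 arrived well into Part 2. Under version 3, Table 4 footnote 5 required the Day 1 predose coagulation test for former sham children. This stands.

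**Conclusion.** The mismatch is real: Section 16.2.2.6 calls for a coagulation check before dosing, and the version 4 schedule makes it conditional on Part 2 Day 1 with nothing at End of Part 1 to replace it. A site following the tables could dose with a last scheduled result D to D+27 days old, assuming same-day rollover on Part 1 Day D.

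The point is minor. It applies only to Day 1 visits held under version 4, and that number is unknown and may be zero. Confidence in the practical consequence is moderate.

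Three stronger readings should be resisted:

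- A reader might infer that children were dosed untested. The documents show only that the schedule permits it.
- A reader might infer that the Part 2 coagulation baseline would be missing. Section 16 defines it as the last nonmissing value before the first Part 2 dose, so it would fall back to Part 1 Screening.
- A reader might extend the point to urine total protein or to the SAP Section 5.2 shift tables. Section 16.2.2.6 does not cover urine protein, and Section 5.2 states in advance how unknown baselines are counted.

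**What to change.** Add coagulation to footnote 5 of Tables 3 and 4 as a predose test on Part 2 Day 1, run at the local laboratory and reviewed before the injection. Version 3 Table 4 already required the test predose and locally for former sham children. Alternatively, add coagulation to the End of Part 1 laboratory tests, as version 2 did. The schedule copied into SAP Section 1.4 should match.

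The cost is a footnote edit in two tables, for a local test already in the Part 2 panel. The practical downside is that Day 1 dosing waits for the local result.

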16.3. Efficacy

16.3.1. Analysis Population

The exploratory analysis of efficacy will be performed on the intent-to-treat population. The intent-to-treat population is defined as all subjects who are randomized and receive at least 1 dose of study treatment or sham procedure in Part 1.

16.3.2. Methods of Analysis

For continuous endpoints, the mean change from baseline will be estimated with 95% confidence limits. For categorical outcomes, the proportion of subjects attaining a specified category will be estimated. Selected endpoints may be pooled across subsets as appropriate.

16.3.2.1. Sibling SMA Data Collection

If any subject has or had a sibling(s) with SMA and if consent is given, data for the sibling(s) will be collected at Day 1 and at the End of Study Evaluation/Early Termination Visit. Data to be collected from siblings with SMA will be nonbiologic and noninvasive and will include historical data for *SMN2* gene copy number and sibling treatment history.

16.4. Pharmacokinetics

16.4.1. Analysis Population

The PK population will include all subjects who are randomized and have at least 1 evaluable postdose or postsham-procedure PK sample.

16.4.2. Methods of Analysis

Plasma PK parameters, as applicable, and Nusinersen concentrations in plasma and CSF for the PK population will be summarized using descriptive statistics and, where warranted, presented graphically.

16.5. Immunogenicity

16.5.1. Analysis Population

The analysis population for immunogenicity will include all subjects with available immunogenicity data.

16.5.2. Methods of Analysis

Results from the immunogenicity analyses for anti-Nusinersen plasma antibody status and titer will be summarized at the specified visits.

16.6. Interim Analyses

No formal interim analyses are planned. However, if the Sponsor decides to terminate Part 1 early, data prior to the unblinding of the first subject in Part 1 may be archived; no analyses are

CONFIDENTIAL

The information contained herein may not be used, disclosed, or published without the written consent of Biogen MA Inc.

planned to be conducted based on the archived data. Full analysis of Part 1 data will be done following database lock at the end of Part 1.

16.7. Sample Size Considerations

Since this study is exploratory, sample size determination will not be based on power consideration. The sample size considered for this study will allow exploration of safety, tolerability, and selected efficacy endpoints in the selected study population.

CONFIDENTIAL

The information contained herein may not be used, disclosed, or published without the written consent of Biogen MA Inc.

17. ETHICAL REQUIREMENTS

The Sponsor, [REDACTED] (the contract research organization [CRO] for this study), and the Investigator must comply with all instructions, regulations, and agreements in this protocol and applicable International Council for Harmonisation (ICH) and Good Clinical Practice (GCP) guidelines and conduct the study according to local regulations.

The Investigator may delegate responsibilities for study-related tasks where appropriate to individuals sufficiently qualified by education, training, and experience, in accordance with applicable ICH and GCP guidelines. The Investigator should maintain a list of the appropriately qualified persons to whom significant study-related duties have been delegated.

17.1. Declaration of Helsinki

This study will be performed in alignment with the ethical principles outlined in the Declaration of Helsinki.

17.2. Ethics Committee

The Investigator must obtain ethics committee approval of the protocol, ICF, and other required study documents prior to starting the study. The Sponsor (or designee) will submit documents on behalf of the investigational sites in countries other than the US.

If the Investigator makes any changes to the ICF, the Sponsor (or designee) must approve the changes before the ICF is submitted to the ethics committee. A copy of the approved ICF must be provided to the Sponsor (or designee). After approval, the ICF must not be altered without the agreement of the relevant ethics committee and the Sponsor (or designee).

It is the responsibility of the Investigators to ensure that all aspects of institutional review are conducted in accordance with current applicable regulations.

The Sponsor (or designee) must receive a letter documenting ethics committee approval, which specifically identifies the protocol, protocol number, and ICF, prior to the initiation of the study. Protocol amendments will be subject to the same requirements as the original protocol.

A progress report must be submitted to the ethics committee at required intervals and not less than annually.

At the completion or termination of the study, the investigational site must submit a close-out letter to the ethics committee and the Sponsor (or designee).

